Hematologic	Continue at the same dose level.	Continue at the same dose level.	Withhold dose until toxicity is Grade ≤ 2 , or has returned to baseline, then resume treatment at the same dose level.	Withhold dose until toxicity is Grade ≤ 2 , or has returned to baseline, then reduce the dose by 1 level and resume treatment or discontinue at the discretion of the investigator.

Specific GI toxicities potentially related to PF-07265028 should be managed according to the dose modifications described in [Table 9](#).

090177e198aafefApproved\Approved On: 22-Nov-2021 20:52 (GMT)

Table 9. Dose Modifications for PF-07265028 Related GI Toxicity

Grade 1	Grade 2	Grade 3*	Grade 4
Continue at the same dose level and, institute standard of care supportive measures at the discretion of the investigator.	Continue at the same dose level and institute standard of care supportive measures at the discretion of the investigator. If recurrent and intolerable, withhold dose until toxicity is Grade ≤ 1 , or has returned to baseline, then resume treatment at the next lower dose level	Withhold dose until toxicity is Grade ≤ 1 , or has returned to baseline, then resume treatment at the same dose level or reduce the dose by 1 level at the discretion of the investigator. If recurrent, withhold dose until toxicity is Grade ≤ 1 , or has returned to baseline, then reduce the dose by 1 level.	Withhold dose until toxicity is Grade ≤ 1 , or has returned to baseline, then reduce the dose by 1 level and resume treatment, or discontinue at the discretion of the investigator. If recurrent, permanently discontinue treatment

*Nausea, vomiting, or diarrhea must persist at Grade 3 despite optimal supportive care to require dose modification.

Note: Cycle will not be extended to cover for the missing dose.

Note: For management of GI iRAEs see [Appendix 3 Section 10.3](#).

Note: Participants with confirmed Hy's Law must be discontinued.

Table 10. Dose Modifications for PF-07265028 Related QTcF Prolongation

QTcF >480 ms \leq 500 ms	QTcF >500 ms	Recurrent QTcF >500 ms	QTcF >500 ms or >60 ms change from baseline, and Torsade de pointes or polymorphic ventricular tachycardia or signs/symptoms of serious arrhythmia

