6.5.2. Dose Reductions

No dose reductions are permitted for sasanlimab.

Following dosing interruption or cycle delay due to treatment-related toxicity, the PF-07265028 dose may need to be reduced when treatment is resumed.

No specific dose adjustments are recommended for Grade 1 or 2 treatment-related toxicity. However, investigators should always manage their participants according to their medical judgment based on the particular clinical circumstances.

Participants experiencing recurrent and intolerable treatment-related Grade 2 toxicity may resume dosing at the next lower dose level once recovery to Grade ≤ 1 or baseline is achieved.

Dose reduction of PF-07265028 by 1 and, if needed, 2 dose levels will be allowed depending on the type and severity of toxicity encountered. Participants requiring more than 2 dose reductions will be discontinued from the treatment and entered into the Follow-up phase, unless otherwise agreed between the investigator and the sponsor. All dose modifications/adjustments must be clearly documented in the participant's source notes and CRF.

Once a dose has been reduced for a given participant, all subsequent cycles should be administered at the reduced dose level, unless further dose reduction is required. Intraparticipant dose re-escalation is not allowed.

Participants experiencing a DLT may resume dosing at the next lower dose level (if applicable) once adequate recovery is achieved, and in the opinion of the investigator and sponsor, the participant is benefiting from therapy.

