Grade 1 Grade 1 AST or ALT > ULN to 3.0 x ULN if baseline was normal, >1.5-3.0 x baseline if baseline was abnormal; and/or Total bilirubin > ULN to 1.5 x ULN if baseline was normal, >1.0-1.5 x baseline if baseline was abnormal	-Continue study treatment	-Continue liver function monitoring -If worsens: Treat as Grade 2 or 3 - 4.
Grade 2 AST or ALT >3.0 to ≤5 x ULN if baseline was normal, >3.0-5.0 x baseline if baseline was abnormal; and/or total bilirubin >1.5 to ≤3 x ULN if baseline was normal, >1.5-3.0 x baseline if baseline was abnormal	-Withhold study treatment -Increase frequency of monitoring to every 3 days.	-If returns to Grade ≤1: -Resume routine monitoring; resume study treatment. -If elevation persists >5 to 7 days or worsens: -Treat as Grade 3 to 4.
Grade 3 to 4 AST or ALT >5 x ULN if baseline was normal, >5.0 x baseline if baseline was abnormal; and/or total bilirubin >3 x ULN if baseline was normal, >3 x baseline if baseline was abnormal	-Permanently discontinue study treatment -Increase frequency of monitoring to every 1 to 2 days -1.0 to 2.0 mg/kg/day prednisone or equivalent -Add prophylactic antibiotics for opportunistic infections -Consult gastroenterologist/hepatologist -Consider obtaining MRI/CT scan of liver and liver biopsy if clinically warranted	-If returns to Grade ≤1: -Taper steroids over at least 1 month -If does not improve in >3 to 5 days, worsens or rebounds: -Add mycophenolate mofetil 1 gram (g) twice daily -If no response within an additional 3 to 5 days, consider other immunosuppressants per local guidelines.

090177e198aafefApproved\Approved On: 22-Nov-2021 20:52 (GMT)

Renal irAEs		
Grade of Creatinine Increased (NCI-CTCAE v5.0)	Initial Management	Follow-up Management
Grade 1 Creatinine increased > ULN to 1.5 x ULN	-Continue study treatment	-Continue renal function monitoring -If worsens: Treat as Grade 2 to 3 or 4.
Grade 2 to 3 Creatinine increased >1.5 and ≤6 x ULN	-Withhold study treatment -Increase frequency of monitoring to every 3 days -1.0 to 2.0 mg/kg/day prednisone or equivalent. -Add prophylactic antibiotics for opportunistic infections -Consider renal biopsy	-If returns to Grade ≤1: -Taper steroids over at least 1 month, and resume study treatment following steroids taper. -If worsens: -Treat as Grade 4.

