10.5. Appendix 5: Genetics

Use/Analysis of DNA

- Genetic variation may impact a participant's response to study intervention, susceptibility to, and severity and progression of disease. Therefore, where local regulations and IRBs/ECs allow, a blood sample will be collected for DNA analysis.
- The scope of the genetic research may be narrow (eg, 1 or more candidate genes) or broad (eg, the entire genome), as appropriate to the scientific question under investigation.
- The samples may be analyzed as part of a multistudy assessment of genetic factors involved in the response to PF-07265028 alone and in combination with sasanlimab or study interventions of this class to understand treatments for the disease(s) under study or the disease(s) themselves.
- The results of genetic analyses may be reported in the CSR or in a separate study summary, or may be used for internal decision making without being included in a study report.
- The sponsor will store the DNA samples in a secure storage space with adequate measures to protect confidentiality.
- The samples will be retained as indicated:
 - Retained samples for banking will be stored indefinitely or for another period as per local requirements.
 - Participants may withdraw their consent for the storage and/or use of their Retained Research Samples at any time by making a request to the investigator; in this case, any remaining material will be destroyed. Data already generated from the samples will be retained to protect the integrity of existing analyses.
 - Samples for genetic research will be labeled with a code. The key between the code and the participant's personally identifying information (eg, name, address) will be held securely at the study site.

10.6. Appendix 6: Liver Safety: Suggested Actions and Follow-Up Assessments and Study Intervention Rechallenge Guidelines

Potential Cases of Drug-Induced Liver Injury

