Humans exposed to a drug who show no sign of liver injury (as determined by elevations in transaminases) are termed “tolerators,” while those who show transient liver injury but adapt are termed “adaptors.” In some participants, transaminase elevations are a harbinger of a more serious potential outcome. These participants fail to adapt and therefore are “susceptible” to progressive and serious liver injury, commonly referred to as DILI. Participants who experience a transaminase elevation above $3 \times$ ULN should be monitored more frequently to determine if they are “adaptors” or are “susceptible.”

In the majority of DILI cases, elevations in AST and/or ALT precede TBili elevations ($>2 \times$ ULN) by several days or weeks. The increase in TBili typically occurs while AST/ALT is/are still elevated above $3 \times$ ULN (ie, AST/ALT and TBili values will be elevated within the same laboratory sample). In rare instances, by the time TBili elevations are detected, AST/ALT values might have decreased. This occurrence is still regarded as a potential DILI. Therefore, abnormal elevations in either AST OR ALT in addition to TBili that meet the criteria outlined below are considered potential DILI (assessed per Hy’s law criteria) cases and should always be considered important medical events, even before all other possible causes of liver injury have been excluded.

The threshold of laboratory abnormalities for a potential DILI case depends on the participant’s individual baseline values and underlying conditions. Participants who present with the following laboratory abnormalities should be evaluated further as potential DILI (Hy’s law) cases to definitively determine the etiology of the abnormal laboratory values:

- Participants with AST/ALT and TBili baseline values within the normal range who subsequently present with AST OR ALT values $>3 \times$ ULN AND a TBili value $>2 \times$ ULN with no evidence of hemolysis and an alkaline phosphatase value $<2 \times$ ULN or not available.

For participants with baseline AST OR ALT OR TBili values above the ULN, the following threshold values are used in the definition mentioned above, as needed, depending on which values are above the ULN at baseline:

- Preexisting AST or ALT baseline values above the normal range: AST or ALT values >2 times the baseline values AND $>3 \times$ ULN; or $>8 \times$ ULN (whichever is smaller).

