A potential DILI (Hy's law) case becomes a confirmed case only after all results of reasonable investigations have been received and have excluded an alternative etiology.

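### For the lower corner of the Hy's Law range with early recovery, the hepatic irAE table resumes study treatment while a note under Table 9 requires discontinuation once the case is confirmed, and no passage says which governs

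*Protocol*

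**What the plan says.** **Hepatic irAE table (Protocol Section 10.3.5, Grade 2).** The row covers "AST or ALT >3.0 to ≤5 x ULN if baseline was normal", joined by and/or to "total bilirubin >1.5 to ≤3 x ULN if baseline was normal". A combined rise is therefore expressly included. Study treatment is withheld. If values return to Grade 1 or lower, the table says "Resume routine monitoring; resume study treatment". If the elevation lasts beyond 5 to 7 days or gets worse, it is handled as Grade 3 to 4, which means permanent discontinuation. The row neither mentions Hy's Law nor refers to another section.

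**Hy's Law thresholds.** Section 4.3.3.2 lists as a DLT an ALT or AST rise above 3 x ULN with total bilirubin above 2 x ULN, without cholestasis or another explanation. Appendix 6 (Section 10.6) uses the same two thresholds for a normal baseline, "with no evidence of hemolysis and an alkaline phosphatase value" below 2 x ULN or not available. It adds that a potential "case becomes a confirmed case only after all results of reasonable investigations have been received and have excluded an alternative etiology".

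**Consequence.** A note under Table 9 (Section 6.5) says that participants with confirmed Hy's "Law must be discontinued". Table 9 is the table for PF-07265028 related GI toxicity.

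**After a DLT.** Section 6.5.2 says "Participants experiencing a DLT may resume dosing at the next lower dose level (if applicable) once adequate recovery is achieved", on the further condition that the investigator and sponsor consider the participant to be benefiting. Hy's Law events are not excepted.

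**Appendix 6 heading.** It reads "Liver Safety: Suggested Actions and Follow-Up Assessments and Study Intervention Rechallenge Guidelines", but the text beneath it contains no rechallenge guidance.

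**The concern.** One liver event can fall under two instructions that point in opposite directions. A site working from the hepatic irAE table sees an instruction to restart once the laboratory values recover. A site that also finds the Table 9 note sees an obligation to stop if the case is confirmed. The note sits under a GI table and the hepatic table does not point to it, so it is easily missed by someone managing liver tests.

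Participant safety comes first here. This is a first-in-human drug, given in some parts with a PD-1 antibody, and Appendix 6 requires potential Hy's Law cases to be reported as SAEs. There is also an effect on the data. The SAP summarizes AEs leading to withdrawal from study treatment (Section 6.1.2) and treatment exposure (Section 6.8.3). If similar events are resumed at one site and discontinued at another, those summaries partly reflect which passage was applied.

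**Working it through.** The plan states no figure on this point, so the check compares the thresholds and then follows one case through the passages.

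**Inputs (normal baseline, multiples of ULN)**
- irAE Grade 2: AST/ALT >3 to ≤5 and/or bilirubin >1.5 to ≤3 (Section 10.3.5). Above 5 or above 3 respectively is Grade 3 to 4.
- Hy's Law: AST/ALT >3 and bilirubin >2 (Section 4.3.3.2, Appendix 6).

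**Overlap.** Grade the event by the worse of the two tests and require both Hy's Law conditions:
- AST/ALT: (>3 to ≤5) and (>3) gives >3 to ≤5.
- Bilirubin: (>1.5 to ≤3) and (>2) gives >2 to ≤3.

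| AST/ALT | Bilirubin | irAE table | Hy's Law thresholds | Conflict possible |
|---|---|---|---|---|
| 3.1 | 2.1 | Grade 2 | met | yes |
| 4 | 2.5 | Grade 2 | met | yes |
| 5 | 3 | Grade 2 | met | yes |
| 5.1 | 2.5 | Grade 3 to 4 | met | no, both discontinue |
| 4 | 3.1 | Grade 3 to 4 | met | no, both discontinue |
| 3 | 2.5 | Grade 2 | not met | no |
| 4 | 2 | Grade 2 | not met | no |

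The rows marked yes also assume no hemolysis and ALP below 2 x ULN or unavailable. The two rows where both discontinue refer to a confirmed case.

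**One case followed through.** Take ALT 4 x and bilirubin 2.5 x ULN.
1. The irAE table grades it 2 and withholds treatment. Appendix 6 makes it a potential Hy's Law case, with evaluation preferably within 48 hours and SAE reporting.
2. Suppose ALT falls to ≤3 x and bilirubin to ≤1.5 x ULN before the 5-to-7-day rule applies. The irAE table now says to resume. Its trigger is laboratory recovery alone.
3. Confirmation has a different trigger: all reasonable investigations back, and alternative causes excluded. Appendix 6 does not say whether dosing may resume in the meantime.
4. If the case is confirmed, the Table 9 note requires discontinuation, possibly of a participant already restarted.
5. If the event fell in Cycle 1 of Part 1 and was judged a DLT, Section 6.5.2 conditionally permits resumption one level lower.

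**Can a Grade 2 irAE also be a confirmed case?** That depends on whether immune hepatitis from a study drug counts as an alternative cause. Section 6 defines study intervention as both PF-07265028 and sasanlimab, which suggests it does not. Section 4.3.3.2, however, lists another drug capable of causing the injury as an excluding reason, and does not say how sasanlimab counts when PF-07265028 is being assessed. The documents leave this open.

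**The case against.** The strongest reply is that the rules can be read together. Section 10.3.5 is guidance organized by grade, whereas the Table 9 note is specific and mandatory and applies only to confirmed cases, so it would ordinarily limit the general table. Section 6.5.2 gives a conditional permission, which does not contradict an obligation. Section 8 also requires safety issues to be discussed with the sponsor immediately to decide on continuation, so a site would not act alone. On this view only a cross-reference is missing.

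Part of this stands. Section 6.5.2 on its own contradicts nothing; it merely omits an exception. The note does not touch a potential case that turns out to have another cause. Sponsor discussion lowers the chance of an uncorrected restart. But precedence of the note is the reader's inference: the protocol does not state it, and the note does not name the drug to be stopped. Nor does precedence settle what happens before confirmation.

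A reader might also infer more than the text supports:
- **That the whole Hy's Law range is restarted.** It is not. Above 5 x ULN for AST/ALT or 3 x ULN for bilirubin, and for persisting or worsening elevations, the irAE table also discontinues permanently.
- **That three outcomes are printed, one being resumption at the same dose.** The hepatic table gives no dose on resumption, and Section 6.5.3 refers the need for reduction to Section 6.5.2. Resuming and resuming lower are therefore compatible.
- **That two thirds of Grade 2 bilirubin events are affected.** (3 − 2)/(3 − 1.5) = 0.67 is a ratio of band widths. It ignores the joint AST/ALT rise and the recovery limit.
- **That all 240 planned participants are exposed to the conflict.** Section 6.5.1 describes the algorithms as developed for sasanlimab irAEs, so their use in the monotherapy parts is not established there.

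**Conclusion.** The conflict is real but narrow. For participants with normal baseline it concerns AST/ALT >3 to ≤5 x ULN together with bilirubin >2 to ≤3 x ULN, no hemolysis, ALP below 2 x ULN or unavailable, and recovery to Grade 1 or lower before the persistence rule applies. In that region one passage says to resume and another says to discontinue if the case is confirmed.

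Four things are left unstated: which rule governs; whether the note covers PF-07265028, sasanlimab or both; whether study-drug immune hepatitis is an alternative cause; and whether dosing may resume while a potential case awaits confirmation.

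The head-on contradiction rests on one assumption, that an event managed as a Grade 2 irAE can also become a confirmed Hy's Law case. If the sponsor reads it otherwise, the gap before confirmation and the unclear drug scope remain. Events should be rare, and no frequency can be derived from the documents. Abnormal baselines use different multiples in the two places and are not sized here. Because this is a participant-safety rule in a first-in-human study, it should be corrected even though few participants are likely to be affected.

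**What to change.** Reconcile the note under Table 9 (Section 6.5), Section 6.5.2, the Grade 2 row of the hepatic irAE table (Section 10.3.5) and Appendix 6, so that one stated rule applies when AST/ALT and bilirubin jointly meet the Appendix 6 thresholds. The text should state:
- which drug or drugs the rule covers;
- what applies while a potential case awaits confirmation;
- whether immune hepatitis attributed to a study drug counts as an alternative cause;
- how the rule relates to resumption after a DLT under Section 6.5.2.

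Cross-refer the rule from the hepatic irAE table, and make the Appendix 6 heading and its content agree on rechallenge. Which clinical rule applies is for the sponsor to decide; this point favors neither.

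The cost is protocol wording in an amendment. Sample size, endpoints and planned analyses do not change.

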10.4. Appendix 4: Contraceptive and Barrier Guidance

10.4.1. Male Participant Reproductive Inclusion Criteria

Male participants are eligible to participate if they agree to the following requirements during the intervention period and for at least 93 days after the last dose of study intervention, which corresponds to the time needed to eliminate reproductive safety risk of the study interventions (eg, 5 terminal half-lives) *plus* an additional 90 days (a spermatogenesis cycle):

- Refrain from donating sperm

PLUS either:

- Be abstinent from heterosexual intercourse as their preferred and usual lifestyle (abstinent on a long term and persistent basis) and agree to remain abstinent

OR

- Must agree to use contraception/barrier as detailed below:
 - Agree to use a male condom when engaging in any activity that allows for passage of ejaculate to another person and should also be advised of the benefit for a female partner to use a highly effective method of contraception as a condom may break or leak when having sexual intercourse with a woman of childbearing potential who is not currently pregnant.

10.4.2. Female Participant Reproductive Inclusion Criteria

A female participant is eligible to participate if she is not pregnant or breastfeeding, and at least 1 of the following conditions applies:

- Is not a WOCBP (see definitions below in [Section 10.4.3](#)).

OR

- Is a WOCBP and using a contraceptive method that is highly effective (with a failure rate of <1% per year), preferably with low user dependency, as described below, during the intervention period and for at least 6 months after the last dose of study intervention, which corresponds to the time needed to eliminate any reproductive safety risk of the study intervention. As for participants using a highly effective method that is user dependent, this contraception method must be used together with a second effective method of contraception, as described below. The investigator should evaluate the effectiveness of the contraceptive method in relationship to the first dose of study intervention.

A WOCBP agrees not to donate eggs (ova, oocytes) for the purpose of reproduction during this period. The investigator should evaluate the effectiveness of the contraceptive method in relationship to the first dose of study intervention.

The investigator is responsible for review of medical history, menstrual history, and recent sexual activity to decrease the risk for inclusion of a woman with an early undetected pregnancy.

10.4.3. Woman of Childbearing and Non-Childbearing Potential

A woman is considered fertile following menarche and until becoming postmenopausal unless permanently sterile (see below).

If fertility is unclear (eg, amenorrhea in adolescents or athletes) and a menstrual cycle cannot be confirmed before the first dose of study intervention, additional evaluation should be considered.

Women in the following categories are not considered WOCBP:

1. Premenopausal female with 1 of the following:

- Documented hysterectomy;
- Documented bilateral salpingectomy;
- Documented bilateral oophorectomy.

For individuals with permanent infertility due to an alternate medical cause other than the above, (eg, mullerian agenesis, androgen insensitivity), investigator discretion should be applied to determining study entry.

Note: Documentation for any of the above categories can come from the site personnel's review of the participant's medical records, medical examination, or medical history interview. The method of documentation should be recorded in the participant's medical record for the study.

2. Postmenopausal female:

- A postmenopausal state is defined as no menses for 12 months without an alternative medical cause. In addition,
 - A high FSH level in the postmenopausal range must be used to confirm a postmenopausal state in women under 60 years of age and not using hormonal contraception or HRT.
 - A female on HRT and whose menopausal status is in doubt will be required to use 1 of the non-estrogen hormonal highly effective contraception methods if they wish to continue their HRT during the study. Otherwise, they must discontinue HRT to allow confirmation of postmenopausal status before study enrollment.

